Study Duration:	
24 months total
 
 • 18 months to recruit/enroll over two influenza seasons • 6 weeks participation for most subjects • Maximum of 6 months participation for a subset of approximately 100 participants at Duke during 2017-2018 flu season • 4.5 months to perform analysis and laboratory assays after the end of each flu season • A subset of 60 subjects from year 1 will be revaccinated with same influenza vaccine product during the year 2 influenza season at Duke
Participant Duration:	
 • 43 days for 780 participants • 181 days for approximately 100 participants at Duke for longer term immunogenicity studies (Year 1 only) • Approximately 14 months for 60 participants in the repeat vaccination sub-study (at Duke only)
Description of Study Procedures:	
This is a prospective, randomized, blinded clinical trial to assess the safety and immunogenicity of adjuvanted inactivated influenza vaccine (aIIV3) versus High-Dose inactivated influenza vaccine (IIV3-HD) in subjects aged ≥65 years. Participants aged 65 to 79 years will be randomized (1:1) to receive either aIIV3 or IIV3-HD using a permuted block randomization scheme stratified by Lead and Contributing Site(s) for at least 704 subjects. A separate permuted block will be allocated for at least 176 subjects who are age 80 years or older, thus achieving an overall N≥880.
 
Vaccine reactogenicity will be assessed for 8 days post-

	
injection and compared between the two groups using identical paper diaries. Serious adverse events and events of clinical interest will be assessed through 42 days post-vaccination and compared between the two groups.
 
Health-related quality of life will be assessed at baseline before vaccination, at day 3 and day 9 post-vaccination. Perceptions of the vaccination study experience and adverse event monitoring experience will be assessed at days 9 and 29 post-vaccination.
 
Vaccine strain-specific serum hemagglutination inhibition antibody titers will be measured from blood samples collected pre- and 29 days post-immunization for all participants and for approximately 100 subjects at Duke on Day 181 (Year 1 only).
 
Vaccine reactogenicity, serious adverse events (SAEs) and events of clinical interest, health related quality of life, and vaccine strain-specific serum hemagglutination inhibition antibody titers pre- and 29 days post-immunization will be measured in a subset of 60 subjects in a repeat vaccination sub-study (at Duke only). Subjects in the second year of the repeat vaccination sub-study will be assigned to receive the same vaccination that they received the first year.

Objectives:
	
Primary Objectives:
 
 1. To compare the proportions of moderate/severe injection-site pain after aIIV3 and IIV3-HD in the full study population 
 a. Hypothesis: the proportion of subjects who have moderate/severe injection site pain within the first week post-vaccination will be non-inferior for aIIV3 compared to IIV3-HD in the full study population 2. To compare serious adverse events and events of clinical interest after aIIV3 and IIV3-HD in the full study population and by age-group 3. To compare the seroconversion rate for the H3N2 influenza A strain after aIIV3 and IIV3-HD in the full study population

	
a. Hypothesis: the seroconversion rate for the H3N2 influenza A strain in the full study population after aIIV3 will be non-inferior to IIV-HD
 
Secondary Objectives
 
 1. To compare the proportions of local and systemic reactions (other than moderate/severe injection site pain) after aIIV3 and IIV3-HD in the full study population and by age-group (65-79 years and ≥80 years) 2. To describe and compare changes in health-related quality of life after aIIV3 and IIV3-HD in the full study population and by age-group 3. To compare serum hemagglutination inhibition (HAI) antibody titers after aIIV3 and IIV3-HD for each of the three influenza vaccine strains contained in the respective vaccine for that season in the full study population and by age (except for seroconversion for the H3N2 strain in the full study population) 
Exploratory Objectives:
 
 1. To describe how the reactogenicity events affect health-related quality of life after IIV3 and IIV3-HD in the full study population and by age-group 2. To describe and compare participant perceptions of the vaccination experience 3. To describe participant perceptions of methods of adverse event monitoring in older adults receiving influenza vaccines. 4. To describe injection site pain immediately after vaccination after aIIV3 and IIV3-HD 5. To describe and compare the proportions of immediate adverse events after aIIV3 and IIV3-HD and unsolicited adverse events in the full study population and by age-group (65-79 years and ≥80 years) 6. To describe factors (e.g., statin use) associated with reactogenicity to aIIV3 and IIV3-HD 7. To describe the safety of aIIV3 and IIV3-HD after repeat administration of the same product over 2 consecutive influenza seasons in a subset of subjects 8. To describe the relationship between reactogenicity and immunogenicity for aIIV3 and IIV3-HD 9. To explore factors (e.g., statin use) associated with immunogenicity for aIIV3 and IIV3-HD
--	---

	
10. To describe the immunogenicity of aIIV3 and IIV3-HD after repeat administration of the same product over 2 consecutive influenza seasons in a subset of subjects
 
11. To assess changes in serum hemagglutination inhibition at 1 month after aIIV3 and IIV3-HD vaccination and at 6 months after vaccination in a subset of subjects


Outcome Measures:
	
Primary:
 
 1. Comparison of the proportion of subjects reporting moderate/severe injection site pain within the first week post-vaccination in both treatment groups. 2. The frequency and descriptions of serious adverse events and adverse events of clinical interest observed in the two treatment cohorts 3. H3N2 HAI seroconversion: The proportion of subjects achieving H3N2 seroconversion at day 29 (an HAI titer \geq 1:40 at day 29 if the baseline titer is $<$ 1:10 or a minimum four-fold rise in HAI titer if the baseline titer is \geq 1:10) in the respective season's vaccine 
Secondary
 
 1. Comparison of local and systemic reactions within the first week post-vaccination in both treatment groups. 2. Change in scores on the Late Life Function & Disability Instrument (Year 1 only), EuroQOL 5 dimensions-5 level (EQ-5D-5L) and EuroQOL visual analogue scale (EQ VAS) pre-vaccination and post-vaccination will be compared between the vaccination groups and age groups. 3. HAI titers: 
 a. The proportion of subjects achieving seroconversion at day 29 (an HAI titer \geq 1:40 at day 29 if the baseline titer is $<$ 1:10 or a minimum four-fold rise in HAI titer if the baseline titer is \geq 1:10) for H1N1 and influenza B and H3N2 (by age group only) in the respective season's vaccine b. Proportion of subjects with a seroprotective HAI titer (\geq 1:40) pre- and post-immunization at day 29 for each IIV antigen in the respective season's vaccine The geometric mean HAI titer (GMT) for each IIV antigen in the respective season's vaccine c. The geometric mean HAI titer (GMT) for each IIV antigen in the respective season's vaccine

	
Exploratory:
 
 1. Associations between moderate/severe local and systemic reactogenicity events and quality of life outcomes in the full study population and by age group 2. Comparison between vaccination groups of proportion of participants with negative and positive perceptions of the vaccination experience based on responses to the Perceptions of Vaccination Experience questionnaire 3. Proportion of participants with difficulty performing adverse event monitoring based on responses to questions to the Perceptions of Vaccination Experience questionnaire 4. Mean injection site pain scores immediately after vaccination in both vaccination groups using the Faces Pain Scale 5. Compare the frequency and descriptions of immediate reactogenicity and immediate serious adverse events and adverse events of clinical interest between vaccination groups. 6. Associations between reactogenicity and demographic, co-morbidity and medication factors from subjects' medical histories, including statin use 7. Compare changes in local and systemic reactions in subjects who receive vaccine in both study years 8. Associations between HAI titers and moderate/severe local and systemic reactogenicity events. 9. Associations between HAI titers and demographic, co-morbidity and medication factors in subjects' medical histories including statin use 10. Comparison of seroprotection and seroconversion as defined by HAI titers and geometric mean HAI titers in subjects who receive vaccine in both study years 11. Comparison of seroprotection and seroconversion as defined by HAI titers and geometric mean HAI titers between 1 month and 6 months in the same subjects (Year 1 only)

Estimated Time to Complete Enrollment:
	
Approximately 6 months for enrollment during each of two consecutive flu seasons, for an overall duration of 18 months

1 BACKGROUND

1.1 Background

The Advisory Committee on Immunization Practices (ACIP) has long recommended influenza vaccination for older persons ≥ 65 years to prevent influenza and its complications¹. In addition to standard inactivated influenza vaccine (IIV), several new licensed influenza vaccines are available for use in older adults, including FLUAD®: an adjuvanted trivalent inactivated influenza vaccine (aIIV3) and Fluzone® High-Dose IIV3 (IIV3-HD). The ACIP has not indicated a preferential recommendation for any of the influenza vaccine preparations approved for older adults².

Older adults are at high risk for influenza-related morbidity and mortality due to immunosenescence (decreased immune responses with age), multimorbidity, specific age-related diseases (e.g, congestive heart failure, chronic lung disease) and age-related changes in compensatory physiologic responses to inflammatory states³⁻⁶. Although the incidence of influenza is usually higher in younger adults and children than older adults, 90% of influenza-related deaths occur in older adults⁷. From 1976-2007, the estimated average number of annual influenza-associated deaths with underlying respiratory and circulatory causes in persons aged ≥ 65 years was 21,098 with a maximum number of 43,727⁸. The risk of hospitalization associated with influenza is highest in persons aged ≥ 65 years⁹. Influenza is also associated with functional decline, reduced quality of life, and disability in older adults¹⁰.

Influenza vaccination is an important intervention to prevent influenza and its complications in older adults, but the immunogenicity and effectiveness of influenza vaccines are suboptimal in older adults due to immunosenescence¹¹. Vaccine scientists have pursued different strategies to improve the immunogenicity and clinical effectiveness of influenza vaccine in older adults. One strategy is to increase the dose of hemagglutinin antigen in the vaccine¹². The IIV3-HD has four times the dose of hemagglutinin antigen compared to standard-dose IIV3 (IIV3-SD). Compared with IIV3-SD, IIV3-HD is significantly more immunogenic for the influenza A strains and non-inferior for the B strain¹³. Studies have also demonstrated that the IIV3-HD is more effective in preventing influenza than IIV3-SD in older adults^{14,15}. A large randomized controlled trial showed relative vaccine effectiveness of 24% for IIV3-HD compared with IIV3-SD, which equated to 4 fewer cases of laboratory-confirmed influenza per 1000 persons vaccinated after IIV3-HD compared with IIV3-SD¹⁴. Another strategy is to add an adjuvant to the influenza vaccine. The aIIV3 contains the MF59 adjuvant which is a squalene-based, oil-in-water emulsion¹⁶. Non-inferiority of aIIV3 compared with IIV3-SD was demonstrated for all three vaccine strains based on pre-defined thresholds for seroconversion rate differences and geometric mean titer ratios¹³. Observational studies conducted in Europe have found that aIIV3 is more effective in preventing influenza than IIV3-SD¹⁶. A confirmatory, randomized controlled clinical trial in the United States to verify and describe the clinical benefit of aIIV3 is required by the FDA under the accelerated approval regulations¹⁷.

Clinicians and older adult patients now face an important choice between IIV3-SD, IIV-HD3 and aIIV3. The superior immunogenicity (for IIV-HD) and clinical effectiveness of IIV3-HD and aIIV3 may sway the choice towards these products compared with IIV3-SD, but the safety of these vaccines is a key factor in the decision. Although aIIV3, IIV-HD and IIV3-SD appear to have similar proportions of serious adverse events, aIIV3 and IIV3-HD have higher proportions of local and systemic reactions compared with IIV3-SD^{15,18}. However, IIV3-HD and aIIV3 have not been compared directly with regards to safety in the same trial. In separate clinical trials, the

most common moderate/severe injection-site reaction was pain (4.2% aIIV3 and 4% IIV3-HD) and the most common moderate/severe systemic reaction was malaise/fatigue (3.5% aIIV3 and 6.3% IIV3-HD)^{13,18}. These rates of moderate/severe reactions are higher than those reported for IIV3-SD. Moderate/severe reactions are generally those which limit or prevent usual daily activities. For older persons, the ability to independently perform basic activities of daily living (e.g., bathing, dressing, grooming, toileting, eating, mobility) and instrumental activities of daily living (e.g., cooking, housework, traveling, managing money, managing medications) are critical to quality of life. Any reaction that limits or prevent these activities will have a significant impact on health-related quality of life and is likely to be more clinically important than in younger, healthier populations¹⁹⁻²¹.

1.2 Summary and Rationale

The safety profile or immunogenicity of aIIV3 and IIV3-HD have not been compared head-to-head. The decision of which vaccine to use in older adults will be enhanced by a better understanding of the safety and immunogenicity of these vaccines, as well as the relative impact on health-related quality of life, functioning and participant perspectives of the vaccination experience. Furthermore, the best method for collecting information on health-related quality of life, functional status and other non-medically attended adverse events after moderate to severe injection site or systemic reactions is not known. This study will address this gap in knowledge in older adults after vaccination. This study will also add value to pandemic influenza preparedness by providing data on risks and benefits of influenza vaccination in older adults that are not currently available.

2 STUDY OBJECTIVES AND OUTCOME MEASURES

2.1 Study Objectives

2.1.1 Primary Objectives:

1. To compare the proportions of moderate/severe injection-site pain after aIIV3 and IIV3-HD in the full study population
 - a. Hypothesis: the proportion of subjects who have moderate/severe injection site pain within the first week post-vaccination will be non-inferior for aIIV3 compared to IIV3-HD in the full study population
2. To compare serious adverse events and events of clinical interest after aIIV3 and IIV3-HD in the full study population and by age-group
3. To compare the seroconversion rate for the H3N2 influenza A strain after aIIV3 and IIV3-HD in the full study population
 - a. Hypothesis: the seroconversion rate for the H3N2 influenza A strain in the full study population after aIIV3 will be non-inferior to IIV-

2.1.2 Secondary Objectives

1. To compare the proportions of local and systemic reactions (other than moderate/severe injection site pain) after aIIV3 and IIV3-HD in the full study population and by age-group (65-79 years and ≥ 80 years)
2. To describe and compare changes in health-related quality of life after aIIV3 and IIV3-HD in the full study population and by age-group
3. To compare serum hemagglutination inhibition (HAI) antibody titers after aIIV3 and IIV3-HD for each of the three influenza vaccine strains contained in the respective vaccine for that season in the full study population and by age (except for seroconversion for the H3N2 strain in the full study population)

2.1.3 Exploratory Objectives:

1. To describe how the reactogenicity events affect health-related quality of life after IIV3 and IIV3-HD in the full study population and by age-group
2. To describe and compare participant perceptions about the vaccination experience
3. To describe participant perceptions of methods of adverse event monitoring in older adults receiving influenza vaccines.
4. To describe injection site pain immediately after vaccination after aIIV3 and IIV3-HD
5. To describe and compare the proportions of immediate adverse events and unsolicited adverse events after aIIV3 and IIV3-HD in the full study population and by age-group (65-79 years and ≥ 80 years)
6. To describe factors (e.g., statin use) associated with reactogenicity to aIIV3 and IIV3-HD
7. To describe the safety of aIIV3 and IIV3-HD after repeat administration of the same product over 2 consecutive influenza seasons in a subset of subjects
8. To describe the relationship between reactogenicity and immunogenicity for aIIV3 and IIV3-HD
9. To explore factors (e.g., statin use) associated with immunogenicity for aIIV3 and IIV3-HD
10. To describe the immunogenicity of aIIV3 and IIV3-HD after repeat administration of the same product over 2 consecutive influenza seasons in a subset of subjects
11. To assess changes in serum hemagglutination inhibition at 1 month after aIIV3 and IIV3-HD vaccination, and at 6 months after vaccination in a subset of subjects

2.2 Study Outcome Measures

Where possible, all outcome measures will be evaluated and compared between the two treatment groups for the full population and in both age subsets (65-79 years and ≥ 80 years)

2.2.1 Primary Outcome Measures:

1. Comparison of the proportion of subjects reporting moderate/severe injection site pain within the first week post-vaccination in both treatment groups.
2. The frequency and descriptions of serious adverse events and adverse events of clinical interest observed in the two treatment groups.

3. H3N2 HAI seroconversion: The proportion of subjects achieving H3N2 seroconversion at day 29 (an HAI titer \geq 1:40 at day 29 if the baseline titer is $<$ 1:10 or a minimum four-fold rise in HAI titer if the baseline titer is \geq 1:10) in the respective season's vaccine.

2.2.2 Secondary Outcome Measures

1. Comparison of local and systemic reactions within the first week post-vaccination in both treatment groups.
2. Change in scores on the Late Life Function & Disability Instrument (Year 1 only), EuroQOL 5 dimensions-5 level (EQ-5D-5L) and EuroQOL visual analogue scale (EQ VAS) pre-vaccination and post-vaccination will be compared between the vaccination groups and age groups.
3. HAI titers by vaccination group and age group (except for seroconversion to H3N2 strain for the full study population):
 - a. The proportion of subjects achieving seroconversion at day 29 (an HAI titer \geq 1:40 at day 29 if the baseline titer is $<$ 1:10 or a minimum four-fold rise in HAI titer if the baseline titer is \geq 1:10) for H1N1 and influenza B and H3N2 (by age group only) in the respective season's vaccine
 - b. Proportion of subjects with a seroprotective HAI titer (\geq 1:40) pre- and post-immunization at day 29 for each IIV antigen in the respective season's vaccine
 - c. The geometric mean HAI titer (GMT) for each IIV antigen in the respective season's vaccine

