 - Note: In Year 2, subjects participating in the sub-study on repeat vaccination will sign a new consent form
- Determine if subject will participate in long term immunogenicity sub-study or repeat vaccination sub-study (Year 1 only)
- Review and confirm study eligibility
- Perform cognitive assessment with the Mini-Cog tool²² (and RUDAS if needed)(Appendix B,C)
 - Scores 3-5 on MiniCog will be eligible
 - Scores 0-1 on MiniCog will be ineligible
 - Scores of 2 on MiniCog: person will undergo further screening with RUDAS. If person scores 23 or higher (range = 0-30), they will be eligible.
 - Potential participants may have low scores on the cognitive screening tests and be ineligible for the study. In this case, the study doctor or designee will review the results with the individual and recommend follow-up with the individual's health care provider.

- Obtain information on preferred method of contact for follow-up (telephone or email reminder), and obtain contact info for caregiver/significant other
- Obtain demographic data
 - Age, gender, race/ethnicity, language spoken, contact information, education, insurance payer, employment status, living alone or not
- Obtain medical history including chronic conditions, hearing and sensory impairment, chronic pain
- Obtain concomitant medications, including use of statin medications.
- Obtain influenza immunization history for the previous two seasons (identify whether vaccine used was FLUAD, Fluzone-High Dose, some other inactivated influenza vaccine, or unknown, and indicate if this information came from the patient or their chart)
- Obtain vital signs including oral temperature, blood pressure, and pulse; and height and weight in order to calculate body mass index (BMI)
- Obtain baseline health-related quality of life assessments prior to vaccination (Section 5.5)
- Obtain answers to first two questions of perceptions of the vaccination experience questionnaire
- Perform pre-vaccination baseline immediate reactogenicity assessment (Appendix D)
- Obtain one tube of blood (~10 mL) prior to vaccination for serologic analysis (Section 5.7.1)
 - If unable to draw blood, subject will remain in study
 - If less than 1 mL of processed serum is collected, it is a protocol deviation
- Randomize study participant to allV3 or IIV3-HD administration (Section 5.2.1)

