6 LABORATORY ANALYSES

6.1 Influenza Hemagglutination Inhibition (HAI) Assay

Influenza Hemagglutination Inhibition (HAI) Assays will be performed on sera collected, contingent on additional funding. Briefly, reference wild-type, reassortant, or vaccine virus strains representative of the specific viral antigens included in the 2017-2018 and 2018-2019 influenza vaccine will be used to evaluate the relative levels of all three influenza strain-specific antibodies in participant serum samples collected pre- and 28 days post-vaccination from all study participants and at 181 days post-vaccination in a subset of 100 participants at Duke. To accomplish these activities all participant samples will be interrogated for influenza antibodies against the strains of interest using the influenza hemagglutination inhibition assay (HI). This assay is considered the “gold-standard” measure by which to evaluate seroconversion/seroprotection in response to seasonal influenza vaccination. This assay will be performed in accordance with the Duke Regional Biocontainment Laboratory Virology Unit's fully optimized and approved SOP (RVUSOP004 Influenza HI of Serum Samples). Briefly, test samples will be assayed by HAI as duplicate 2-fold dilution series starting at 1:10. Serum dilutions are then incubated with a concentration of virus verified to possess a known potential for red blood cell (RBC) agglutination. The presence of virus-specific antibodies is visualized via incubation of the virus-serum mixture with a RBC solution; the endpoint titer for a given dilution series is then expressed as the reciprocal of the final dilution in which complete HAI is observed. By convention, seronegative samples are defined as having an endpoint HAI titer < 40 and seropositive samples as having an endpoint titer of $\geq 1:40$; and seroconversion as a 4-fold change in endpoint titer relative to pre-immunization baseline or a change from <10 to $\geq 1:40$ ³⁷.

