7.1.1 Sample Size

Safety: Based on data from prelicensure studies^{4,5,7}, we assume that 5% of older adults have moderate/severe injection-site reactions after aIIV3 or IIV3-HD. We have selected a clinically meaningful non-inferiority margin of 5%. Statistical calculations, without consideration of drop-out, show that with an alpha of 0.025 (one-sided), we would need 668 total subjects (334 subjects in each group across all study sites) to have at least 80% power be able to demonstrate that the proportion of moderate/severe pain was non-inferior after aIIV3 vs. IIV3-HD. Enrollment in this study shall occur during two influenza seasons (2017-18 and 2018-19).

Immunogenicity: Based on data from prelicensure studies^{4,5,7}, we conservatively estimate that 50% of older adults demonstrate seroconversion after vaccination with aIIV3 or IIV3-HD for the H3N2 strain. We have selected a clinically meaningful non-inferiority margin of 10%. Statistical calculations, without consider of drop-out, show that with an alpha of 0.025 (one-sided), we would need 780 total subjects (390 subjects in each group across all study sites) to have approximately 80% power to able to demonstrate that the seroconversion rate after aIIV3 was non-inferior to IIV3-HD.

The total number of subjects needed for this study was derived based on 4 factors: 1) Sample size needed for adequate statistical power to test the safety hypothesis; 2) sample size needed for adequate statistical power to test the immunogenicity hypothesis; 3) potential for subject drop-out; and 4) feasibility of dividing subjects across 2 sites. Based on these considerations, the study aims to enroll at least 880 subjects to assess both the safety and immunogenicity endpoints. The study aims to enroll at least 720 to test only the safety hypothesis.

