7.1.2 Analysis Populations

Full Analysis Population:

- For Primary Objective 1 and Secondary Objective 1, the primary analysis population will be the Full Analysis Population; defined as all subjects who are randomized, vaccinated, and provide at least one day of complete data on the symptom diary.
- For Primary Objective 2 and Secondary Objective 2, the primary analysis population will be the Full Analysis Population; defined as all subjects who are randomized and vaccinated.

Immunogenicity Population:

For Primary Objective 3 and Secondary Objective 3 the primary analysis will be for the Immunogenicity Population; defined as subjects who received vaccine, provide baseline and Visit 4 blood draws of acceptable volume and quality within the protocol-defined time frame with

no protocol violations affecting immunogenicity. Protocol violations affecting the immunogenicity analyses will be defined in the Statistical Analysis Plan (SAP).

The Full Analysis Population is the primary population for analysis unless otherwise stated.

7.1.3 Primary Objective 1

- To compare the proportions of moderate/severe injection site pain after aIIV3 and IIV3-HD in the full study population
 - Hypothesis: the proportion of subjects who have moderate/severe injection site pain within the first week post-vaccination will be non-inferior for aIIV3 compared to IIV3-HD in the full study population

This objective will be assessed using a one-sided non-inferiority test with the alpha level set at 0.025 and non-inferiority margin of 5%.

The null hypothesis is aIIV3 is inferior to IIV3-HD in regards to the proportion of subjects having moderate or severe injection site pain in the first week post vaccination.

$$H_0: aIIV3 - IIV3-HD \geq 0.05 \text{ (5\%)}$$

The alternative hypothesis is aIIV3 is non-inferior to IIV3-HD in regards to the proportion of subjects having moderate or severe injection site pain in the first week post vaccination.

$$H_a: aIIV3 - IIV3-HD < 0.05 \text{ (5\%)}$$

The upper bound of the one-sided binomial confidence interval of the difference will be used to make this assessment.

7.1.4 Primary Objective 2

- To compare serious adverse events and events of clinical interest after aIIV3 and IIV3-HD in the full study population and by age-group

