To compare serum hemagglutination inhibition (HAI) antibody titers after aIIV3 and IIV3-HD for each of the three influenza vaccine strains contained in the respective vaccine for that season in the full study population and by age-group (except for seroconversion for the H3N2 strain in the full study population)

Responses to each influenza antigen will be analyzed, with the exception of seroconversion for H3N2, which is analyzed in Primary Objective 1. The proportion of subjects with seroprotection (pre- and post-immunization) seroconversion (4-fold rise from baseline) in the two treatment groups will be presented along with 95% exact binomial confidence intervals. A 95% confidence interval of the difference in proportions between the treatment groups will also be presented.

The GMTs for each influenza antigen, including H3N2, and 95% confidence boundaries will be presented for both treatment groups. A 95% confidence interval of the difference in GMTs between the treatment groups will also be presented. This information will also be prepared for the subset (N≥176) of subjects 80 or older.

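### The planned interval for the Day 29 seroprotection difference ignores the baseline titer and is therefore wider than it needs to be

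*Combined protocol and SAP*

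**What the plan says.** Section 2.2.2, outcome 3(b), defines seroprotection as a titer of 1:40 or above and asks for the proportion "pre- and post-immunization at day 29 for each IIV antigen in the respective" season's vaccine. Section 7.1.8 sets out the analysis: "The proportion of subjects with seroprotection (pre- and post-immunization) seroconversion (4-fold rise from baseline) in the two treatment groups will be presented", with exact 95% intervals per arm. The comparison between arms is then described: "A 95% confidence interval of the difference in proportions between the treatment groups will also be presented".

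Section 7.1.2 assigns Secondary Objective 3 to the Immunogenicity Population and describes that set in these terms: "defined as subjects who received vaccine, provide baseline and Visit 4 blood draws of acceptable volume and quality within the protocol-defined time frame". It also requires that no protocol violation has affected immunogenicity. There is no criterion on the baseline titer. Age group is the only split named for this outcome. Seroprotection has no margin, test, alpha level or power statement.

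Section 6.1 uses the same cut-off at the assay level: "seronegative samples are defined as having an endpoint HAI titer < 40".

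**The concern.** A subject already at 1:40 or above on Day 1 will in most cases still be there on Day 29, whichever vaccine was given. Baseline status therefore explains part of the variation in the Day 29 outcome. A crude difference leaves that variation in its standard error. Stratifying on baseline status takes it out, using a value the trial must already hold for every analysed subject.

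Subjects who are already protected are to be expected. Earlier seasons' vaccination is not an exclusion (only the current season's is, in section 4.2), and the Visit 1 procedures in section 5.1 say to "Obtain influenza immunization history for the previous two seasons".

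At stake is the precision of one secondary comparison, repeated for each strain and age group. The plan also gives no figure for how often each vaccine brings a subject from below 1:40 up to it.

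**Working it through.** **The plan's own immunogenicity figure.** Seroprotection is not sized. The only immunogenicity sizing is for H3N2 seroconversion (section 7.1.1): "with an alpha of 0.025 (one-sided), we would need 780 total subjects", with 50% in both arms, a 10-point margin and about 80% power. Then n per arm = 2 × 0.5 × 0.5 × (1.960 + 0.842)² / 0.10² = 393, or 786 in total. At 390 per arm the power is 79.8%. The stated 780 is reproduced, so 390 per arm is used below.

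**Assumed inputs, not in the documents.**
- b, the share at 1:40 or above at baseline, the same in both arms: 30%, 50%, 70%.
- Baseline-protected subjects stay at 1:40 or above.
- Among the rest, 60% and 75% reach 1:40 by Day 29.

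**Formulas.**
- Day 29 rate in an arm: P = b + (1 − b)p.
- All-subject difference: (1 − b) × (0.75 − 0.60).
- Crude variance: sum over arms of P(1 − P)/390.
- Stratified variance: (1 − b)² × sum over arms of p(1 − p)/[390(1 − b)]. The baseline-protected stratum contributes nothing.

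**Example, b = 50%.** The rates are 0.875 and 0.800, and the difference is 7.5 points. Crude variance = (0.1094 + 0.1600)/390 = 0.000691. Stratified variance = 0.25 × (0.1875 + 0.2400)/195 = 0.000548. The reduction is 20.6%.

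| b | Difference, both methods (points) | Crude 95% half-width | Stratified half-width | Variance cut | Difference/SE, crude vs stratified |
|---|---|---|---|---|---|
| 30% | 10.5 | 5.8 | 5.4 | 13.5% | 3.53 vs 3.79 |
| 50% | 7.5 | 5.2 | 4.6 | 20.6% | 2.85 vs 3.20 |
| 70% | 4.5 | 4.2 | 3.6 | 26.7% | 2.12 vs 2.48 |

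The crude method would need about 451, 491 and 532 per arm for the same precision (390 divided by 1 minus the cut).

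The stratified formula holds the baseline split at b in each arm. Chance variation in the split adds about b(1 − b) × 0.15²/780 to the variance. At b = 50% that is 0.0000072, and the cut becomes 19.6% instead of 20.6%.

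**Does the gain need a true difference?** No. With the same p in both arms, the cut reduces to b(1 − p)/[b + (1 − b)p]. At b = 50% this is 0.5 × 0.40/0.80 = 25% for p = 0.60, and 0.5 × 0.25/0.875 = 14% for p = 0.75.

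**Subjects below 1:40 at baseline only.** Here the difference is 15 points at every b. The half-width is 1.96 × √[(0.1875 + 0.2400)/n], with n = 390(1 − b) = 273, 195 and 117 per arm, which gives 7.8, 9.2 and 11.8 points. For the 176 planned subjects aged 80 or older, about 88 per arm before losses, it is about 16, 19 and 25 points.

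**The case against.** The strongest case against is that nothing here is wrong. The share of vaccinated older adults at 1:40 or above on Day 29 is a legitimate quantity, and randomization makes its crude difference unbiased. That stands.

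A reader might infer that the planned comparison is defective because already-protected subjects shrink a difference d among the others to (1 − b)d. The arithmetic is right, but this describes which quantity is estimated. It is not a bias. Preferring the difference among the initially unprotected is a choice of target. A reader might also infer that Mantel-Haenszel stratification would undo the shrinkage. It would not: its weights follow stratum size, so it still estimates (1 − b)d. Only the row restricted to subjects below 1:40 shows d. That row has a much wider interval in points, most of all at age 80 or older.

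The companion outcomes also cover much of the ground. Seroconversion is defined relative to baseline, and geometric mean titers have no ceiling at 1:40. On a twofold series from 1:10, a subject below 1:10 or at 1:10 seroconverts exactly by reaching 1:40, so among the unprotected the two outcomes part only at a baseline of 1:20. Pre-vaccination seroprotection is reported by arm, so readers will see b. These points limit the weight of the concern. None of them narrows the crude interval.

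The size is assumed. The documents give no b and no seroprotection rates, and the one planning assumption has the arms equal on seroconversion: "we conservatively estimate that 50% of older adults demonstrate seroconversion after vaccination with aIIV3 or IIV3-HD for the H3N2 strain". With equal arms there is no difference to shrink, but the precision gain remains.

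Lastly, section 7 calls its content summary points and announces a comprehensive SAP, which might specify a baseline adjustment. It is not in the documents, and section 7.1.10 expressly defers only the exploratory analyses to it.

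**Conclusion.** The point holds as one of precision. As written, the Day 29 seroprotection comparison leaves out a baseline value that the analysis population must have. Under the assumptions above, stratifying cuts the variance by 13.5%, 20.6% and 26.7% at b = 30%, 50% and 70%, and narrows the interval by about 7%, 11% and 14%. The true gain depends on b, which may differ by strain and age group, and on how nearly all baseline-protected subjects stay at 1:40 or above. Assay variation could move a few below.

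The documents do not support the reading that the planned difference is biased or invalid, or that a trial conclusion is at risk. Seroprotection is estimated with an interval and not tested, and the primary H3N2 seroconversion comparison is unaffected. This is a minor improvement.

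**What to change.** In section 7.1.8, state that the 95% interval for the Day 29 seroprotection difference will come from an analysis stratified by baseline titer for that antigen (below 1:40 versus 1:40 or above), for example a Mantel-Haenszel risk difference. Say that it estimates the same all-subject difference as the crude analysis. Keep the planned pre- and post-vaccination proportions by arm.

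As a descriptive supplement in 2.2.2(3b) and 7.1.8, report by arm the proportion reaching 1:40 or above among subjects below 1:40 at baseline. Add a note that its interval is wider, particularly in those aged 80 or older.

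The cost is a few sentences of analysis wording and one extra row per antigen. No new samples, data or subjects are needed. Settling it before unblinding avoids a post hoc choice.
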